2.1 Data analysis general information

The data will be analyzed by Novartis personnel.

SAS version 9.4 or later will be used to perform all data analyses and to generate tables, figures and listings.

[REDACTED]

2.1.2 Reports

The outputs will be specified in the Interim CSR TFL shells document.

2.1.3 General analysis conventions

Pooling of centers: Unless specified otherwise, data from all study centers will be pooled for the analysis. Due to expected small size of centers, no center effect will be assessed.

Qualitative data (e.g., gender, race, etc.) will be summarized by means of contingency tables by treatment group; a missing category will be included as applicable. Percentages will be calculated using the number of subjects in the relevant population or subgroup as the denominator.

Quantitative data (e.g., age, body weight, etc.) will be summarized by appropriate descriptive statistics (i.e. mean, standard deviation, median, minimum, and maximum) by treatment group.

Grouping of subjects

Unless otherwise specified, all analyses will be done separately for Phase Ib and Phase II subjects and within each phase by treatment group.

A treatment group is defined by the dose combination of EGF816 and INC280 in the Phase Ib part and by subject group in the Phase II part. Details about the labeling of the treatment groups are provided in the TFL shells document.

For the Phase Ib part, subjects treated with the same initial dose level of EGF816 and INC280 will be pooled into a single treatment group. Both pre and post intra-subject dose escalation data will be listed and summarized together under the initial dose level/treatment group.

For Phase II, summaries and listings will mainly be produced by the 4 groups (Group 1 to Group 4, described in [Section 1.1.2](#)). Subjects will be reported according to the group to which they were assigned at baseline based on their mutation status and prior lines of systemic antineoplastic therapies.

Some efficacy and safety outputs will be produced for subgroups. For details regarding the definition of subgroups and the related analyses, please refer to [Section 2.2.2](#), [Section 2.5.2.4](#), and [Section 2.7.2](#).

2.1.4 General definitions

Investigational drug and study treatment

Investigational drug will refer to the individual compound, i.e. INC280 or EGF816, whereas study treatment will refer to the treatment combination INC280 + EGF816.

The term investigational treatment may also be referred to as study treatment, which is used throughout this document.

Date of first administration of investigational drug

The date of first administration of investigational drug is defined as the first date when a nonzero dose of investigational drug is administered and recorded on the ‘Dosage Administration Record’ (DAR) eCRF. The date of first administration of investigational drug will also be referred to as start of investigational drug or start of study drug.

Date of last administration of investigational drug

The date of last administration of investigational drug is defined as the last date when a nonzero dose of investigational drug is administered and recorded on the DAR eCRF. The date of last administration of investigational drug will also be referred to as end of investigational drug or last date of exposure to the study drug. (Example: A subject had a permanent discontinuation of the study drug on 06-Jan-2015 after being put on a temporary interruption since 01-Jan-2015. In this case the last date of exposure is 31-Dec-2014).

Date of first administration of study treatment

The date of first administration of study treatment is derived as the first date when a nonzero dose of any component of study treatment was administered as per the DAR eCRF. (Example: if first dose of INC280 is administered on 05-Jan-2015, and first dose of EGF816 is administered on 03-Jan-2015, then the date of first administration of study treatment is on 03-Jan-2015).

Date of last administration of study treatment

The date of last administration of study treatment is derived as the last date when a nonzero dose of any component of study treatment was administered as per DAR eCRF. (Example: if the last INC280 dose is administered on 15-Apr-2015, and the last dose of EGF816 is administered on 17-May-2015, then the date of last administration of study treatment is 17-May-2015).

Study day

The study day describes the day of the event or assessment date, relative to the reference start date.

The study day is defined as:

- The date of the event (visit date, onset date of an event, assessment date etc.) – reference start date + 1 if the event is on or after the reference start date;
- The date of the event (visit date, onset date of an event, assessment date etc.) – reference start date if the event precedes the reference start date.

The reference start date for all assessments (e.g. safety, efficacy, PK) is the start of study treatment.

The study day will be displayed in the data listings. If an event starts before the reference start date, the study day displayed on the listing will be negative. The displayed study day might be calculated based on an imputed date (see [Section 5.1](#) regarding imputation rules).

Time unit

A year length is defined as 365.25 days. A month length is 30.4375 days (365.25/12). If duration is reported in months, duration in days will be divided by 30.4375. If duration is reported in years, duration in days will be divided by 365.25.

Baseline

For safety and efficacy evaluations, the last available assessment within 28 days on or before the date of start of study treatment is defined as ‘baseline’ assessment, unless otherwise stated under the related assessment section.

Baseline can be the day before the first administration of study treatment or the same day as first administration of study treatment if a pre-dose assessment/value is available (e.g., ECG, PK samples, samples for biomarkers).

If time is recorded for the first administration of study treatment and for a specific assessment performed on the day of first administration of study treatment, this assessment will be considered as baseline only if the assessment is performed at a time before the first administration of study treatment.

In cases where multiple measurements meet the baseline definition, with no further flag or label that can identify the chronological order, the following rule will be applied: If values are from central and local laboratories, the value from the central assessment will be considered as baseline. If there are multiple values from the same laboratory (local or central), or collected for ECGs or vital signs, then the last value will be considered as baseline.

If subjects have no value as defined above, the baseline result will be missing.

On-treatment assessment/event and observation periods

The overall observation period will be divided into three mutually exclusive segments:

1. *pre-treatment period*: from day of subject’s informed consent to the day before first administration of study treatment
2. *on-treatment period*: from date of first administration of study treatment to 30 days after date of last actual administration of any study treatment (including start and stop date)
3. *post-treatment period*: starting at day 30 + 1 after last administration of study treatment

If a clear assignment to the pre-, on-, or post-treatment period cannot be made, e.g., in case of specific incomplete dates, then the respective data will be assigned to the on-treatment period.

Safety summaries (tables, figures) include only data from the on-treatment period with the exception of baseline data which will also be summarized where appropriate (e.g. change from baseline summaries). In addition, a separate summary for death including on-treatment and post-treatment deaths will be provided. In particular, summary tables for adverse events (AEs) will summarize only on-treatment events, with a start date during the on-treatment period (*treatment-emergent* AEs).

However, all safety data (including those from the post-treatment period) will be listed and those collected during the pre-treatment and post-treatment period will be flagged.

Windows for multiple assessments

In order to summarize ECG data collected over time (including unscheduled visits), the assessments will be time slotted. The following general rule will be applied in creating the assessment windows: If more than 1 assessment is done within the same time window, the assessment performed closest to the target date will be used. If 2 assessments within a time window are equidistant from the target date, then the earlier of the 2 assessments will be used. If multiple assessments occur on the same date then the worst case will be used except for ECGs. Three ECGs are targeted to be measured at the protocol-defined (nominal) time-points. If a subject has more than one measurement at a specific time point, the average of all available measurements associated with the nominal time point will be used for the analysis. Data from all assessments (scheduled and unscheduled), including multiple assessments, will be listed.

Last contact date

The last contact date will be derived for subjects not known to have died at the analysis cut-off [REDACTED] using the last complete date among the following.

Table 2-1 Last contact date data sources

Source data	Conditions
Last known date patient alive collected on the 'Survival information' eCRF	Subject status is reported to be unknown or lost to follow-up
Date of assessment collected on the 'Survival information' eCRF	Subject status is reported to be alive and missing last known date patient alive
Start/end dates of anti-neoplastic therapies administered after study treatment discontinuation	Non-missing medication or procedure term
Study medication start/end dates from DAR eCRF	Non-missing dose; zero doses are allowed
Date of discontinuation from 'End of Treatment' eCRF and 'End of post-treatment phase' eCRF	None
Start/End dates of AE	Non-missing verbatim AE term
Tumor (RECIST) assessment date	Evaluation is marked as 'done'
Laboratory/PK collection dates	Sample collection marked as 'done'
Vital signs, ECG assessment dates	At least one non-missing parameter value
Performance status dates	Non-missing performance status

The last contact date is defined as the latest complete date from the above list or the cut-off date whichever comes first. The cut-off date will not be used for last contact date, unless the subject was seen or contacted on that date. No date post cut-off date will be used. Completely imputed dates (e.g. the analysis cut-off date programmatically imputed to replace the missing end date of a dose administration record) will not be used to derive the last contact date. Partial date imputation is allowed for event (death)/censoring if coming from 'Survival information' eCRF.

The last contact date will be used for censoring of subjects in the analysis of overall survival.

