[figure not shown]
The protocol allows radiotherapy to the bone or central nervous system (CNS), and surgical resection of CNS metastases as well as palliative bone radiotherapy (that is, these will not lead to censoring).

Derivation of new anti-cancer therapy

To determine the use of new anti-cancer therapy, data entered in the following CRFs will be considered [REDACTED]:

- Antineoplastic Therapy Since Discontinuation of Study Treatment – Medication,
- Antineoplastic Therapy Since Discontinuation of Study Treatment – Radiotherapy,
- Antineoplastic Therapy Since Discontinuation of Study Treatment – Surgery.

In addition certain therapies entered in the CRF Prior and Concomitant Medications (domain CM) will be considered, if they were started after start of study treatment.

2.5.2.5 Primary endpoint – Phase II Group 4

Frequencies of treatment-emergent AEs will be calculated to characterize the safety and tolerability of the study treatment. The Safety Set will be used for summary tables.

2.5.2.6 Statistical hypothesis, model, and method of analysis – Phase II Group 4

Adverse events will be analyzed as described in the section on safety analysis, [Section 2.8.1](#).

2.5.2.7 Handling of missing values/censoring/discontinuations – Phase II Group 4

Summary tables for AEs will include events collected in the on-treatment period. If dates are incomplete and no clear assignment to pre-, on-, or post-treatment period can be made, then on-treatment will be assumed (see [Section 5.1.2](#)).

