2.8.1 Adverse events (AEs)

Coding and grading of AEs

Adverse events are coded using the Medical dictionary for regulatory activities (MedDRA) terminology. The grading is done according to the Common Terminology Criteria for Adverse Events (CTCAE). See [Section 5.2](#) in the appendix for further details.

AE summaries

AE summaries will include all AEs occurring during the on-treatment period (see [Section 2.1.4](#)). All AEs collected in the AE eCRF page will be listed along with the information collected on those AEs, e.g. AE relationship to study treatment, AE outcome etc. AEs with start date outside of the on-treatment period will be flagged in the listings.

AEs will be summarized by number and percentage of subjects having at least one AE, having at least one AE in each primary system organ class (SOC) and for each preferred term (PT) using MedDRA coding. A subject with multiple occurrences of an AE will be counted only once in the respective AE category. A subject with multiple CTCAE grades for the same preferred term will be summarized under the maximum CTCAE grade recorded for the event. AE with missing CTCAE grade will be included in the 'All grades' column of the summary tables.

In AE summaries, the primary system organ class will be presented alphabetically and the preferred terms will be sorted within primary SOC in descending frequency. The sort order for the preferred term will be based on their frequency in the 'All subjects' column combining subjects from Phase Ib and Phase II.

The following adverse event summaries will be produced:

- Overview of adverse events and deaths
- AEs regardless of study treatment relationship (including CTC grade 3/4)
- AEs suspected to be study treatment related (including CTC grade 3/4)
- AEs regardless of study treatment relationship leading to discontinuation of study treatment
- AEs suspected to be study treatment related leading to discontinuation of study treatment
- AEs regardless of study treatment relationship requiring dose adjustment or study treatment interruption
- SAEs regardless of study treatment relationship
- SAEs suspected to be study treatment related
- SAEs with fatal outcome

In addition, tables required for ClinicalTrials.gov and EudraCT will be provided (see [Section 2.8.1.2](#)).

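### Treatment-emergent AEs are defined by start date alone, so a pre-dose AE that worsens on treatment drops out of the AE tables unless the worsening has its own dated record, which the SAP does not state

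*SAP*

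**What the plan says.** Section 2.1.4 divides observation into three mutually exclusive periods. Pre-treatment runs "from day of subject’s informed consent to the day before first administration of study treatment". On-treatment runs "from date of first administration of study treatment to 30 days after date of last actual administration of any study treatment". The section then states that "summary tables for adverse events (AEs) will summarize only on-treatment events, with a start date during the on-treatment period", and labels these events treatment-emergent.

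Two later places depend on that definition:

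- Section 2.5.2.5 (Group 4 primary endpoint): "Frequencies of treatment-emergent AEs will be calculated to characterize the safety and tolerability of the study treatment".
- Section 2.8.1 (all AE tables): "AE summaries will include all AEs occurring during the on-treatment period", with a reference back to Section 2.1.4. It adds that "AEs with start date outside of the on-treatment period will be flagged in the listings".

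Section 2.5.2.7, on missing data for Group 4, uses a third wording: "Summary tables for AEs will include events collected in the on-treatment period".

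Section 2.1.4 also has a fallback. It begins "If a clear assignment to the pre-, on-, or post-treatment period cannot be made" and sends such data to the on-treatment period; its example is incomplete dates.

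**The concern.** A start-date rule with no worsening clause does not count an AE that exists at first dose and becomes more severe under treatment. Take grade 1 diarrhoea that starts after consent and reaches grade 3 in cycle 1. If the database holds this as one record, its start date is pre-treatment. The event is then flagged in a listing and missing from the all-grade, grade 3/4 and, where relevant, serious-event tables.

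Two things make this more than a wording matter. The omission can only lower counts, so any error favours the treatment. And for Group 4 the frequency of treatment-emergent AEs is itself the primary safety analysis, so the definition decides what the primary result contains. The same rule serves the secondary safety objective in the other groups.

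Other safety domains in the SAP do allow for an abnormal baseline: laboratory grades and liver criteria (2.8.3), ECG changes (2.8.4.1) and vital signs (2.8.4.2). AEs have no equivalent rule.

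**Working it through.** The plan gives no figure to reproduce. The check compares the rules and then gives a scale.

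**1. Which rule controls.**

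| Place | Test for entry into AE tables | Pre-dose AE, worsened on treatment, one record |
|---|---|---|
| 2.1.4 | start date in the on-treatment period | excluded |
| 2.5.2.7 (Group 4) | collected in the period | could be read either way |
| 2.8.1 | occurring in the period, with reference to 2.1.4 | could be read either way alone; excluded through the reference |

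Section 2.5.2.5 uses the term that 2.1.4 defines, and 2.8.1 points back to 2.1.4 and flags events by start date. The start-date rule therefore most plausibly controls throughout, although 2.5.2.7 leaves room for another reading.

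**2. Whether another rule brings the event back.**

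- The fallback for unclear assignment does not. A complete pre-dose start date is a clear assignment.
- The grade rule in 2.8.1 (several grades for one preferred term are shown at the maximum) does not settle it. It says how to grade an event, not whether a grade increase is a new record with a new start date.

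**3. What follows from the recording convention.**

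- Each grade increase is a new dated record: the new record starts on treatment and is counted, so the grade-related loss is 0.
- One record keeps its pre-dose start date: the event is left out of the AE tables.
- In either case, the SAP does not say how to treat a pre-dose AE that becomes serious on treatment without a grade change.

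**4. What is summarized elsewhere.**

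- Laboratory worsening: worst post-baseline grade whatever the baseline grade, peak ALT/AST, and separate criteria for raised baseline values (2.8.3).
- Deaths: on-treatment and all deaths by system organ class and preferred term (2.8.2).
- Reductions, interruptions and discontinuations with reasons: taken from the dosing record (2.4.1). Reasons for ending treatment: from the disposition page (2.3.3).

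What remains exposed is mainly non-laboratory, non-fatal AEs that start between consent and the day before first dose.

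**5. Scale.** Planned sizes from Section 1.1.2: Group 4 about 30; Groups 1 and 3 at least 40 each. If k subjects are missing from a row, the row falls by k/n.

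- Group 4, k = 1: 1/30 = 3.3 points.
- Group 4, k = 0 to 3 (assumption): 0/30 to 3/30 = 0 to 10 points.
- A group of 40, k = 1: 1/40 = 2.5 points.

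For one preferred-term row, the full k/n applies only if all k subjects share that term and none has another on-treatment record of it.

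**The case against.** The strongest objection is that the loss depends on a fact the SAP does not contain. AE recording rules commonly sit in the protocol or the eCRF guidelines, which are not at hand. If sites open a new record at each grade change, nothing is lost through grade increases. This stands as a limit on size. A reader might infer from Section 2.1.4 that every worsened pre-dose AE is certain to be missing from every AE table; the document does not support that. It does not remove the point, because the SAP states a positive inclusion rule that gives the right result only under a convention it neither states nor cites.

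The objection is also right on coverage. Laboratory toxicity, deaths and dose changes reach other tables, so an ALT rise is a weak example. The tolerability half of Group 4's objective (interruptions, reductions, dose intensity) does not depend on AE start dates.

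A reader might further infer a large effect because many subjects are pretreated and raised ALT or AST was allowed at entry. That does not follow. Conditions ongoing at entry are reported as medical history (2.3.2), and residual toxicity from earlier therapy would ordinarily predate consent. No affected fraction can be taken from the document, and zero must stay in the range.

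Finally, if a record holds only one start date and one maximum grade, the time of worsening may not be recoverable. This stands, and the remedy has to be limited accordingly.

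**Conclusion.** The point holds in conditional form. As written, the rule excludes a worsened pre-dose AE from the AE tables, including Group 4's primary safety analysis, unless the worsening has its own dated record. The direction is certain (any error makes the profile look safer), but the size is not. In Group 4 the understatement of an affected row is 0 to 10 points under the assumption of 0 to 3 subjects, and 0 for grade increases if each is a new record. The events stay visible in the listings. It merits correction before the final database lock because the rule is explicit and touches a primary endpoint; it is not evidence that the reported AE rates are materially wrong.

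**What to change.** In Section 2.1.4, define a treatment-emergent AE as one that starts in the on-treatment period, or that starts before first dose and, during that period, has a recorded increase in CTCAE grade or becomes serious. Limit the derivation to what the records can show:

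- Where grade changes are separate dated records, count the on-treatment record at its grade.
- Where one record holds only a maximum grade and the timing cannot be determined, assign it to on-treatment, in line with the section's existing fallback. An event that ended before first dose stays pre-treatment, as does a non-serious event whose maximum is grade 1, since neither can have worsened on treatment.

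Bring Sections 2.5.2.7 and 2.8.1 to this single definition in place of the three present wordings, and footnote any difference from the primary CSR.

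The cost is a short change of text, one flag derivation and a footnote. AE counts may rise slightly, some single-record events may be counted although they worsened before first dose, and some comparability with the primary CSR is lost. If grade changes are already separate records, the grade clause changes no counts.

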				
2.5.2.2 Statistical hypothesis, model, and method of analysis – Phase II Groups 1, 2, and 3: The Bayesian estimation of the ORR will not be done for the Final CSR; the related specifications were deleted.
 
2.5.2.3 Handling of missing values/censoring/discontinuations – Phase II Groups 1, 2, and 3: Additional specifications of censoring for new anti-cancer therapy were added.
 
2.7.2 Statistical hypothesis, model, and method of analysis (Censoring pattern of OS): reason for death will not be summarized in the OS table, only the number of deaths and censorings.
 
2.8.3 Laboratory data: Shift tables for lab parameters will not be prepared for the final CSR. The analysis of liver function parameters was modified to align with the current Novartis Hepatotoxicity Guideline.
 
2.8.4.1 ECG: Change from baseline in ECG parameters by time point was added.
 
2.8.4.3 ECOG performance status: Summary of performance status by time point was removed.
 
2.11.5 Derivation of resistance mechanism subgroups for Phase Ib subjects: The subgroup categories for T790M & MET status crossed were updated to also include the missing and the individual categories.
 
2.11.6 Biomarker analysis: The biomarker summary by response status (BOR) for MET expression was changed to IHC category (instead of H-score). A summary of PFS by biomarker categories (GCN and IHC) was added. Corresponding graphical displays will be generated for the Phase II treatment groups only (BOR and PFS).
 
5.1.3 Other imputations: the imputation rules for start dates of post-treatment antineoplastic medications were specified in more detail (Table 5-3).
 
6 References: Typo correction in reference Collett D (1994).

Date	Time point	Reason for update	Outcome for update	Section and title impacted (Current)
06-Nov-2020	Prior to DB lock for final analysis	Update of the last contact date definition	Amendment 5: Update of the last contact date for OS	Update Table 2-1 Last contact date data sources. Date of assessment collected on the "Survival information" eCRF will be considered for last contact date, this is aligned with eCRF completion guidelines (last known date patient alive is not required if subject is reported to be alive)
25-Nov-2021	Prior to DB lock for interim CSR analysis	Cancellation of final analysis and CSR	The previous SAP (amendment 5) for the final CSR analysis will be retired in CREDI	Whole document

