Treatment discontinuation due to ‘Disease progression’ without documented progression, i.e. clinical progression based on investigator claim	Date of last adequate assessment	Censored
New anti-cancer therapy given prior to protocol defined progression	Date of last adequate assessment on or prior to starting new anti-cancer therapy	Censored
Death before first PD assessment	Date of death	Progressed

OS

If a subject is not known to have died at the time of the analysis, then OS time will be censored at the date of last known date subject was alive, i.e., last contact date (see [Section 2.1.4](#)). If the tick box for ‘Lost to follow-up’ is ticked on the ‘Survival information’ eCRF or if the time between the last contact date and the [REDACTED] analysis cut-off date is longer than the protocol specified interval between the survival follow-up assessments plus 2 weeks, i.e., 15 weeks for this study ($3 \times 30.4375 + 14 \text{ days} = 91.3125 + 14 \text{ days} = 105.3125 \text{ days} \approx 15 \text{ weeks}$), subjects OS time will be censored for ‘Lost to follow-up’.

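### Table 2-1 has no row for a survival-form record with status alive and the last-known-alive date filled in, so the OS censoring rule drops that contact (minor correction)

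*SAP*

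**What the plan says.** SAP section 2.1.4 derives a last contact date for subjects not known to have died. Two rows of Table 2-1 draw on the survival form:

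- Source: "Last known date patient alive collected on the 'Survival information' eCRF". Condition: "Subject status is reported to be unknown or lost to follow-up".
- Source: "Date of assessment collected on the 'Survival information' eCRF". Condition: "Subject status is reported to be alive and missing last known date patient alive".

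The remaining rows are post-treatment anti-cancer therapy, dosing, discontinuation, AE, tumor assessment, laboratory/PK, vital sign/ECG and performance status dates. The text below the table states: "The last contact date is defined as the latest complete date from the above list or the cut-off date whichever comes first". It adds: "The last contact date will be used for censoring of subjects in the analysis of overall survival".

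Section 2.7.3 gives the OS rule for a subject not known to have died: "then OS time will be censored at the date of last known date subject was alive, i.e., last contact date". It assigns the censoring reason lost to follow-up if the box is ticked on the form, or if the gap from last contact to cut-off exceeds the survival follow-up interval plus 2 weeks.

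The amendment history (entry of 06-Nov-2020) explains why the assessment date was brought in: under the eCRF completion guidelines, "last known date patient alive is not required if subject is reported to be alive".

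**The concern.** The two survival-form conditions do not cover every record that carries usable evidence of life. If the site reports the subject alive and also completes the last-known-alive date, the first row fails on status and the second fails because the date is not missing. Both dates on that form then drop out, and the last contact date falls back to whatever other source is latest.

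Once a subject is in survival follow-up, few other data are likely to be collected, so the fallback can be earlier. Section 2.7.1 counts every death up to the efficacy cut-off, so only survivors lose follow-up. Early censoring of this kind depends on outcome and pushes the Kaplan-Meier OS estimate downward. It can also change the censoring reason (alive or lost to follow-up), which section 2.7.2 plans to examine and list. Section 2.7.3 equates the censoring date with the last known date alive, yet in this case the table ignores the field that records it.

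**Working it through.** **1. Truth table of the two survival-form rows.** Inputs: the two conditions in Table 2-1.

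| Status on form | Last-known-alive date | Row that applies |
|---|---|---|
| Alive | Missing | Assessment-date row |
| Alive | Filled | None |
| Unknown or lost to follow-up | Filled | Last-known-alive row |
| Unknown or lost to follow-up | Missing | None |

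The last line loses nothing: there is no last-known-alive date to use, and an assessment with status unknown or lost is not evidence of life. The only combination that discards a documented survival contact is alive with the date filled.

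**2. The plan's lost-to-follow-up window (section 2.7.3).** 3 × 30.4375 + 14 = 91.3125 + 14 = 105.3125 days, and 105.3125 / 7 = 15.04 weeks. The plan's figure of about 15 weeks is reproduced.

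**3. Effect of losing one form.** Assume survival contacts one interval (91.3125 days) apart and no later date from any other row. A contact g days before cut-off is replaced by one g + 91.3125 days before cut-off. The reason changes to lost to follow-up when g + 91.3125 > 105.3125, that is, when g > 14.

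| Dropped contact, days before cut-off | Remaining gap, days | Reason as written |
|---|---|---|
| 0 | 91.3 | Alive |
| 14 | 105.3 | Alive (at the limit) |
| 30 | 121.3 | Lost to follow-up |
| 60 | 151.3 | Lost to follow-up |
| 91.3 | 182.6 | Lost to follow-up |

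A subject contacted alive more than 14 and up to 105.3 days before cut-off would therefore be relabelled. The follow-up lost is 91.3 / 30.4375 = 3 months.

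**4. Effect on 24-month OS.** The SAP gives no figures for this, so every input is an assumption: n = 40, exponential OS with median 30 months, follow-up of 24 to 42 months at cut-off, median treatment duration 10 months, 4,000 simulated trials. The share of off-treatment survivors affected was set at 10%, 25% and 50%; none of these rates comes from the SAP.

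| Loss per affected survivor | None affected | 10% | 25% | 50% |
|---|---|---|---|---|
| All survival forms lost, censored 1 month after treatment (about 21 months lost) | 57% | 56% | 54–55% | 51% |
| Latest form only (3 months lost) | 57% | 57% | 57% | 57% |

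The range at 25% reflects separate runs. In the one-form case the shift was under 0.5 points, and the estimate stayed at 57% even with 100% affected. This is expected: with at least 24 months of follow-up, losing 3 months matters at 24 months only for survivors followed for less than 27 months.

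For scale, the sampling error at n = 40, ignoring censoring, is √(0.57 × 0.43 / 40) = 0.078. That gives a 95% interval of roughly ±15 points.

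**The case against.** The uncovered combination is the unexpected one. The completion guidelines do not require the date for a subject reported alive, so the field should usually be blank and the assessment-date row then works. Whether the form even permits the combination cannot be seen from the SAP. The table takes the latest date over all sources and all forms, so one completed field loses one form, and an earlier or later form or any other post-treatment source limits the damage. OS is a secondary, single-arm endpoint described by Kaplan-Meier with no test. Finally, section 2.7.3 makes the intention clear enough that a programmer might query the table.

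Most of this stands, and it settles the size. It does not remove the gap. Not required is not the same as never filled, and a condition that the date be missing presupposes that some alive records have it. An intention expressed in section 2.7.3 does not amend the table that a program will follow.

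A reader might go further and infer that survivors in general are censored early, or that reported OS is materially biased downward. The documents do not support that. The fall to 51% needs half of off-treatment survivors to have the optional date filled on every survival form and to have no later date from any other source.

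**Conclusion.** The point holds as a narrow drafting error in a stated rule: followed literally, Table 2-1 ignores a survival contact that section 2.7.3 says should set the censoring date. OS is censored too early only where that contact is later than every other source in the table. The lost-to-follow-up label is wrong only where the remaining gap also exceeds 105.3 days.

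The number of affected records is unknown and may be small. If one form is lost, the cost is about 3 months of follow-up, with a negligible effect on 24-month OS; the main harm is then the wrong censoring reason. A fall of 1 to 6 points is a worst case under the simulation assumptions above, with 10% to 50% of off-treatment survivors losing all survival forms and having no later source. At the 10% end, the shift of 1 point is small beside a standard error of about 8 points. Deaths, ORR and the Group 4 safety endpoints are unaffected. This is a minor correction.

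**What to change.** Reword the conditions of the two survival-form rows in Table 2-1:

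- Last-known-alive date: use it whenever it is recorded and status is alive, unknown or lost to follow-up.
- Assessment date: keep the present condition, status alive with the last-known-alive date missing.

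Every alive record that carries a usable date then has a row, and the table agrees with section 2.7.3. It is not necessary to take the later of the two dates for alive subjects. If a site entered a last-known-alive date earlier than the assessment, that rule would credit follow-up beyond the date the site recorded.

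Before database lock, count the records with status alive and the date filled, and note for how many subjects the OS censoring date or reason changes. The cost is one table condition, one program condition and one data query. The change can only recover documented contacts.
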